5.3. Other Analysis Sets

5.3.1. Consented Safety Analysis Set

Analysis set limited to patients who gave consent among the safety analysis set

5.3.2. Consented Efficacy Analysis Set

Analysis set limited to patients who gave consent among the efficacy analysis sets

5.4. Subgroups

Subgroup analyses of safety will be performed for the following patient characteristics. Descriptions in brackets indicate the levels of subgroups, and the underlined level indicates the standard level for calculation of risk ratio.

- Hepatic impairment [absent, present, unknown]
- Hepatic impairment [absent, mild, moderate, severe, unknown (presence unknown or severity unknown)]
- Renal impairment [absent, present, unknown]
- Renal impairment [absent, mild, moderate, severe, unknown (presence unknown or severity unknown)]
- Age [<15 years, ≥15 years]
- Age [\leq 65 years, \geq 65 years]
- Age [<18 years, ≥18 years]
- Age [\leq 65 years, \geq 65 to \leq 75 years, \geq 75 years]
- Pregnancy [absent, present] * Female only

Subgroup analyses of safety will be performed for the following other factors:

Contraindications for coadministration/precautions for coadministration [both absent, precautions for coadministration present, contraindications for coadministration present] Patients with precautions for coadministration and patients with contraindications for coadministration may overlap. For patients with precautions for coadministration and patients with contraindications for coadministration, events after the start of coadministration will be included.

• Complicated with HIV infection and concomitantly using anti-HIV therapy including ritonavir or cobicistat [absent, present] * Specifically, patients concomitantly using ritonavir or cobicistat will be classified as present and other patients as absent.

Patients possibly contraindicated in the package insert of this drug (hereinafter referred to as contraindicated patients) will be extracted based on separately specified criteria and subgroup analysis of safety will be performed.

Subgroup analyses of efficacy will be performed for the following patient characteristics. Unless otherwise specified, analysis will be performed for Efficacy Analysis Sets 1 and 3. Descriptions in brackets indicate the levels of subgroups, and the underlined level indicates the standard level for calculation of risk ratio and hazard ratio.

- Combination of admission status at the start of treatment with this drug [inpatient, outpatient] and risk factors for aggravation [risk factors present, risk factors absent, risk factors unknown]. To be performed in Efficacy Analysis Set 1.
- History of use of drugs for the treatment of infection caused by SARS-CoV-2 [history of use absent, history of use present, unknown]
- Number of days from the onset of symptoms of infection caused by SARS-CoV-2 to the start of treatment with this drug [within 3 days, 4 or 5 days, 6 days or more, unknown] If the onset of symptoms and the start of treatment with this drug are on the same day, the number of days will be 0.
- Symptoms and severity of infection caused by SARS-CoV-2 at the start of treatment with this drug [no symptoms, mild, moderate I, moderate II, severe, symptoms or severity unknown]
- Number of risk factors for aggravation of infection caused by SARS-CoV-2 [none, 1, 2, 3, 4, number unknown, unknown]. If there are risk factors but the number is unknown, the patient will be classified as "number unknown." If it is not known that there are risk factors, the patient will be classified as "unknown."
- SARS-CoV-2 vaccination history [present, absent, unknown]
- Number of SARS-CoV-2 vaccination doses (vaccination on or before the day before the start of treatment with this drug) [none, 1, 2, 3, 4 or more, unknown]
- Hepatic impairment [absent, present, unknown]

- Hepatic impairment [absent, mild, moderate, severe, unknown (presence unknown or severity unknown)]
- Renal impairment [absent, present, unknown]
- Renal impairment [absent, mild, moderate, severe, unknown (presence unknown or severity unknown)]
- Age [<15 years, ≥15 years]
- Age [<65 years, ≥65 years]
- Pregnancy [absent, present] * Female only

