#### 8.2.2. Exclusion criteria

There are no exclusion criteria for this study.

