# 8.3.2. Presence/absence of pregnancy (only for women)

The presence/absence of pregnancy from the start date of administration to the end of the observation period should be recorded.

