5.2. Efficacy Analysis Set

Efficacy Analysis Set 1 will consist of the population excluding patients who meet any of the conditions 1, 2, 3, 4, and 5 in Section 5.1 and the conditions shown below.

- Efficacy cannot be evaluated appropriately because the condition for evaluating efficacy is not met
 (description in the report, "efficacy not evaluable")
 Condition: No adverse events are reported, the status of hospitalization is not reported, and both the
 presence or absence of worsening of severity after the start of treatment with this drug and the
 presence or absence of symptoms on the end date of the observation period are not reported.
- 2. Disease not subject to the study (description in the report, "disease not subject to the study") Condition: The disease name is other than infection caused by SARS-CoV-2.
- 3. Inadequate treatment period or dose (description in the report, "inadequate administration") Condition: Nirmatrelvir has not been administered.

Efficacy Analysis Set 2 will exclude patients who meet any of the following conditions from Efficacy Analysis Set 1.

4. The patient was not an outpatient at the start of treatment with this drug (description in the report, "other than outpatient at the start of treatment")

Condition: The patient was not an outpatient at the start of treatment with this drug.

Specific examples of identification methods for Efficacy Analysis Sets 1 and 2 are provided in Section 10.1 Table 1.

Efficacy Analysis Set 3 will exclude patients who meet the following conditions from Efficacy Analysis Set 2.

- 5. No risk factors for aggravation at the start of treatment with this drug (description in the report, "no risk factors for aggravation")
 - Condition: The patient does not meet any of the following risk factors for aggravation. If the age is unknown, it will be considered that the condition for risk factors for aggravation is not met. Similarly, when BMI cannot be calculated, smoking status is unknown or not provided, and medical history is unknown or not provided, it will be considered that each condition is not satisfied.
 - ≥60 years of age

- BMI $> 25 \text{ kg/m}^2$
- Smoking status "present" (a rough guide for "present": current smoking at the start of treatment with this drug [smoking within 30 days] and having smoked at least 100 cigarettes in their lifetime)

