6.4. Covariates

In Study C4671005, subgroup analyses of COVID-19-related hospitalization or death (all causes) reported up to Day 28, an efficacy endpoint, were performed for age, sex, race, BMI, serology, viral load, comorbidities, and number of comorbidities. The results were consistent with those in the whole mITT population in many subgroups and the incidence was significantly or more decreased in the subgroups with a large number of subjects or with a high incidence (Study C4671005, Interim Clinical Study Report). These will not be used as covariates in this study.

While the impact of viral variants and SARS-CoV-2 vaccination history on efficacy has not been evaluated in clinical studies, they are potential covariates.

Since HIV-infected patients may concomitantly use anti-HIV therapy including ritonavir with this drug, this is a potential covariate for the safety of this drug.

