8.1.3. Binary variables

For binary variables, patients falling into each binary category will be summarized in terms of frequency and proportion. When a confidence interval is calculated for a proportion, the two-sided 95% confidence interval (exact method) will be calculated.

When a comparison for proportion is made between subgroups, the risk ratio and its 95% confidence interval will be calculated. In addition, the risk ratio and its 95% confidence interval will be graphically presented.

If a test is performed, Fisher's exact test will be used for the relationship with nominal scale data and Cochran-Armitage test (exact method) for the relationship with ordinal scale data. However, if it is difficult to perform the exact method, a chi-square test or Cochran-Armitage test with normal approximation will be used as an alternative to the exact method.

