8.1.4. Time (to event) data

Kaplan-Meier's method will be used to determine the median, 1st quartile, and 3rd quartile. The time point incidence will be calculated on Days 3, 5, 7, 14, 21, and 28 after the start of treatment with this drug (the start date of treatment will be defined as Day 1). Confidence intervals will be estimated using the log-log transformation (corresponding to specifying a loglog under the conftype option in the proc lifetest statement of the SAS®, lifetest procedure). In addition, Kaplan-Meier plots will be prepared.

When time data are compared between subgroups, the hazard ratio of events and its 95% confidence interval will be calculated using Cox proportional hazard model (Breslow method for handling ties). In addition, the hazard ratio and 95% confidence interval will be graphically presented.

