8.2.3.3. Subgroup analyses

The number and proportion of patients who experienced at least 1 adverse reaction will be tabulated by factor specified in Section 5.4. In addition, risk ratios of the incidence of adverse reactions between subgroups will be calculated as described in Section 8.1.3. However, if there is a category with less than 10 patients and it is determined difficult after reconsideration of the classification of categories, the risk ratio for the category will not be calculated. Similar analyses will be performed for adverse reactions with PTs of dysgeusia, taste disorder, diarrhoea, vomiting, nausea, decreased appetite, and rash by each of the following factors.

Descriptions in brackets indicate the levels of subgroups, and the underlined level indicates the standard level for calculation of risk ratio.

- Hepatic impairment [absent, present, unknown]
- Hepatic impairment [absent, mild, moderate, severe, unknown (presence unknown or severity unknown)]
- Renal impairment [absent, present, unknown]
- Renal impairment [absent, mild, moderate, severe, unknown (presence unknown or severity unknown)]
- Age [<15 years, \ge 15 to <65 years, \ge 65 years]
- Age [<18 years, ≥18 years]
- Age [\leq 65 years, \geq 65 to \leq 75 years, \geq 75 years]
- Pregnancy [absent, present] * Female only
- Contraindications for coadministration/precautions for coadministration [both absent, precautions for coadministration present, contraindications for coadministration present] Patients with precautions for coadministration and patients with contraindications for coadministration may overlap. For patients

with precautions for coadministration and patients with contraindications for coadministration, events after the start of coadministration will be included.

 Complicated with HIV infection and concomitantly using anti-HIV therapy including ritonavir or cobicistat [absent, present] * Specifically, patients concomitantly using ritonavir or cobicistat will be classified as present and other patients as absent.

Adverse reactions will be summarized in terms of number and proportion by each of the following factors among the factors specified in Section 5.4 for each SOC and PT.

- Hepatic impairment [absent, present]
- Hepatic impairment [absent, mild, moderate, severe]
- Renal impairment [absent, present]
- Renal impairment [absent, mild, moderate, severe]
- Age [<15 years, \ge 15 to <65 years, \ge 65 years]
- Age [<18 years, \ge 18 years]

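### The pregnancy subgroup is limited by sex but not by age, so its crude ratios mix pregnancy with age

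*SAP*

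**What the plan says.** SAP 5.4 gives the factor in the same words in its safety list and its efficacy list: "Pregnancy [absent, present] * Female only". SAP 8.2.3.3 repeats it twice, once for the ratios on selected adverse reactions and once for the tables by system organ class and preferred term. SAP 8.2.4.7 has no list of its own and takes its factors from 5.4.

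Nothing else narrows the comparator:

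- Protocol 8.2.2: "There are no exclusion criteria for this study".
- Protocol 8.3.2, for women without an age limit: "The presence/absence of pregnancy from the start date of administration to the end of the observation period should be recorded".
- SAP 8.1.3, binary endpoints: "When a comparison for proportion is made between subgroups, the risk ratio and its 95% confidence interval will be calculated".
- SAP 8.1.4, time-to-event endpoints: "the hazard ratio of events and its 95% confidence interval will be calculated using Cox proportional hazard model". Neither section states an adjustment or a stratification.
- SAP 6.4, after a list of factors that includes age: "These will not be used as covariates in this study".

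SAP 5.2 counts "≥60 years of age" among the risk factors for aggravation. SAP 8.2.3.3 and 8.2.4.7 allow a ratio to be dropped "if there is a category with less than 10 patients" and regrouping does not help.

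**The concern.** The sex restriction is there because men cannot be pregnant. The same reason applies to females outside reproductive age, yet they stay in *absent*. Pregnant patients fall in a limited age band, while the comparator spans all ages. A crude ratio between the two levels then reflects pregnancy and age together.

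This matters most for worsening, death, and hospitalization or death, because the SAP treats older age as prognostic for aggravation. If older women do worse, the comparator's risk is raised and pregnancy looks safer than it is. The final analysis supports the re-examination application (SAP 3), and calculated ratios are also plotted (SAP 8.1.3, 8.1.4), so a reader could take a low value as reassurance.

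**Working it through.** The documents give no figure for this comparison: no age distribution, no number of pregnant patients and no age-specific event rates. The inputs below are assumptions, shown over a range, except the 7.8% reaction rate, which comes from the sample size section.

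**1. Bias of the crude ratio.** Let r be the risk in non-pregnant females of reproductive age, RR_preg the true pregnancy ratio, w the share of *absent* past reproductive age, and RR_age the older-to-younger risk ratio.

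- Risk in *present* = RR_preg × r
- Risk in *absent* = (1 − w) × r + w × RR_age × r
- Crude ratio = RR_preg / (1 + w × (RR_age − 1))

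When events are rare the hazard ratio behaves in nearly the same way. With RR_preg = 1.5:

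| w | RR_age 0.5 | 1 | 1.5 | 2 | 3 |
|---|---|---|---|---|---|
| 0.3 | 1.76 | 1.50 | 1.30 | 1.15 | 0.94 |
| 0.5 | 2.00 | 1.50 | 1.20 | 1.00 | 0.75 |
| 0.7 | 2.31 | 1.50 | 1.11 | 0.88 | 0.625 |

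For example, with w = 0.5 and RR_age = 3: 1.5 / (1 + 0.5 × 2) = 0.75. With a mild age effect the bias is small: w = 0.3 and RR_age = 1.2 give 1.5 / 1.06 = 1.42.

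**2. When the ratio reverses.** The crude ratio falls below 1 when RR_age > 1 + (RR_preg − 1) / w.

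- True ratio 1.5: RR_age above 2.67, 2.00 and 1.71 for w = 0.3, 0.5 and 0.7.
- True ratio 2: RR_age above 4.33, 3.00 and 2.43.

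**3. After the fix.** Restricting *absent* to reproductive age sets w = 0, and the formula returns RR_preg. Stratifying by age removes the same bias, because strata with no pregnant patients contribute nothing to a Mantel-Haenszel risk ratio or to the pregnancy coefficient of a stratified Cox model.

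**4. Precision.** Assume 1500 females, 7.8% with an adverse reaction in the comparator and a true ratio of 1.5, so p1 = 0.117. The standard error of the log ratio is √[(1 − p1)/(n·p1) + (1 − p0)/(m·p0)], with n pregnant and m comparators.

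- n = 10, m = 1490: 1.2 expected events, 95% CI about 0.27 to 8.3.
- n = 30, m = 1470: 3.5 expected events, 95% CI about 0.55 to 4.1.
- n = 30, comparator halved to m = 735: √(0.883/3.51 + 0.922/57.33) = √(0.2516 + 0.0161) = 0.517, and exp(1.96 × 0.517) ≈ 2.76, giving about 0.54 to 4.1.

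Halving the reference group barely changes the interval.

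**The case against.** Several points on the other side stand.

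- **Size.** A reader might infer that the ratio mainly contrasts young with old women, or that it will reverse a real risk. The documents do not support that: it needs an age mix and age-specific rates that they do not give, and under mild inputs 1.5 becomes only 1.42.
- **Direction for adverse reactions.** The documents do not say how reactions vary with age. If younger women report more, the ratio is inflated, as the RR_age 0.5 column shows.
- **Remedy.** A reader might think that age adjustment could not repair the comparison because there are no pregnant patients at older ages. Stratification does repair it, by the argument in step 3. This is ordinary confounding by age.
- **Efficacy Analysis Set 3.** Every woman of known age 60 or over enters on the age criterion, which raises w. Younger women enter only with another risk factor, which may narrow the risk gap. The net effect is unknown.
- **Sparse events.** If the risk of hospitalization or death were 1% (assumed), 30 pregnant patients would have no event with probability 0.99^30 = 0.74. Sparse data could then dominate whichever comparator is used.
- **Consequence.** SAP 4 calls the testing exploratory and sets no decision rule. Protocol 8.9 already concedes limited control of confounding. Protocol 10 has each pregnancy exposure reported and followed to outcome individually, so pregnancy safety does not rest on this ratio.

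These points limit the weight of the concern but do not remove it. A wide interval does not reveal a mismatched comparator. The under-10 rule withholds only the ratio: incidences by pregnancy status are still tabulated, and the organ class and preferred term tables carry no such rule.

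**Conclusion.** The point holds as a cheap improvement. As written, *absent* includes females of any age and nothing in the plan separates age from pregnancy. For effectiveness endpoints the ratio is biased downward if older women have higher risk. With a true ratio of 1.5 and half of the comparator past reproductive age, it reads 1.00 at an older-to-younger risk ratio of 2 and reverses only above that; all three inputs are assumptions. For adverse reactions the direction is unknown. Reversal is possible but not shown to be likely.

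The underlining that marks the reference level is not visible for this item in the text available, so *absent* as reference is inferred. Taking *present* instead would invert the ratio and leave the mixing unchanged.

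**What to change.** In SAP 5.4 (safety and efficacy lists) and SAP 8.2.3.3 (both lists), change the note on the pregnancy factor to: females aged 15 to 49 years only. The range should be fixed in advance and not derived from the pregnant patients observed. Fifteen is already an age cut in the SAP; 49 is a proposed upper limit that the sponsor may replace with another stated value. List any pregnant patient outside the range separately. SAP 8.2.4.7 needs no edit, since it refers to 5.4. The descriptive pregnancy item in SAP 8.2.2.1 can stay because no ratio is formed there.

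Alternatively, keep the factor and stratify the pregnancy ratio by age. If the SAP is closed, the restricted comparison can be added as an additional analysis under 8.2.3.4 and 8.2.4.8, with a footnote to the unrestricted ratio.

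The cost is one line in the definition and the program, using age already collected, and a smaller reference group. Age differences within 15 to 49 remain, as do differences in other risk factors, and the comparison stays exploratory and imprecise.

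### The co-medication risk ratios in SAP 5.4 and 8.2.3.3 use overlapping levels, so neither ratio can be attributed to one kind of co-drug alone

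*SAP*

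**What the plan says.** SAP 5.4 lists one safety factor for co-medication with the levels "both absent, precautions for coadministration present, contraindications for coadministration present". It adds that "Patients with precautions for coadministration and patients with contraindications for coadministration may overlap", and on which events count: "For patients with precautions for coadministration and patients with contraindications for coadministration, events after the start of coadministration will be included". SAP 8.2.3.3 repeats the same levels and notes in both of its factor lists.

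For the factors in 5.4, SAP 8.2.3.3 states that "risk ratios of the incidence of adverse reactions between subgroups will be calculated as described in Section 8.1.3". This covers any adverse reaction, with similar analyses for seven named preferred terms. The second list gives counts and proportions by SOC and PT. The method in SAP 8.1.3 is: "When a comparison for proportion is made between subgroups, the risk ratio and its 95% confidence interval will be calculated". The ratios and intervals are also to be plotted. No adjustment is described.

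Neither section defines a precaution-only level, a level for patients on both kinds of drug, or a hierarchy between the two.

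**The concern.** A three-level factor with a ratio for each exposed level invites the reader to attribute each ratio to its own exposure. Here a patient on both kinds of co-drug sits in both exposed levels. If contraindicated co-drugs raise the risk of reactions, part of that excess appears in the precautions row and could be read as a signal for precaution drugs. In the other direction, any effect of precaution drugs enters the contraindications row. Because the exposed levels share patients and events, two raised ratios are not two separate pieces of evidence. What is at stake is the attribution of a safety signal in a subgroup table; no primary conclusion depends on it.

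**Working it through.** **Plan's own figure.** There is none on this point. The documents state no overlap share, no co-drug risk and no expected ratio.

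**Reference level.** SAP 8.2.3.3 says "the underlined level indicates the standard level for calculation of risk ratio". The underline for this factor does not survive in the text available. Both absent is inferred on two grounds: it is the only level that shares no patients with the other two, and absent is the marked level where the underline does survive, in "Hepatic impairment [ absent , mild, moderate, severe, unknown (presence unknown or severity unknown".

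**Identity.** Let f be the share of the precautions level that also takes a contraindicated drug. All ratios are against both absent. Then

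RR(precautions present) = (1 − f) × RR(precaution only) + f × RR(both).

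The departure from the precaution-only ratio is f × [RR(both) − RR(precaution only)]. It is zero only if nobody overlaps or the added contraindicated drug brings no extra risk. With g as the share of the contraindications level that also takes a precaution drug, the mirror form is

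RR(contraindications present) = (1 − g) × RR(contraindicated only) + g × RR(both).

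**Illustration (f and the risks are assumptions).** Set RR(precaution only) = 1.0:

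| Overlap f | RR(both) = 1.5 | RR(both) = 2 | RR(both) = 3 |
|---|---|---|---|
| 5% | 1.025 | 1.05 | 1.10 |
| 10% | 1.05 | 1.10 | 1.20 |
| 20% | 1.10 | 1.20 | 1.40 |

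For example, at f = 20% and RR(both) = 2: 0.8 × 1.0 + 0.2 × 2.0 = 1.20.

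**With counts.** Assume 1500 patients with both absent and 1200 in the precautions level, of whom 240 overlap. Assume a baseline risk of 7.8%, borrowed from the sample-size rationale (SAP 2.2), and doubled risk in the overlap.

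- Both absent: 1500 × 0.078 = 117 events.
- Precaution only: 960 × 0.078 = 74.88 events.
- Overlap: 240 × 0.156 = 37.44 events.
- Planned row: (74.88 + 37.44)/1200 = 0.0936, and 0.0936/0.078 = 1.20. The standard error of log RR is √(1/112.32 − 1/1200 + 1/117 − 1/1500) ≈ 0.126, so the 95% CI is 0.94 to 1.54.
- Precaution-only row: RR 1.00, standard error √(1/74.88 − 1/960 + 1/117 − 1/1500) ≈ 0.142, 95% CI 0.76 to 1.32.

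**Does another rule in the SAP separate the exposures?**

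- Counting only events after the start of coadministration does not. A reaction after both drugs have started counts in both levels.
- The small-category rule in 8.2.3.3 lets a ratio be dropped "if there is a category with less than 10 patients and it is determined difficult after reconsideration of the classification of categories". It could remove the contraindications ratio while the same patients stay in the precautions level.
- The listing of adverse reactions in contraindicated patients leaves the ratios unchanged.

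**The case against.** The strongest reply is that nothing is miscalculated. The level is labelled as precaution drugs being present, not as precaution drugs only, and the overlap is disclosed beside it. For that label the row is right: it describes everyone taking a precaution drug. This stands. A reader might infer that the SAP reports a wrong precaution-only ratio, but it plans no such ratio. What is missing is the row that would answer that question.

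Second, the SAP says only that patients may overlap. True overlap could be near zero, and the intervals in the worked example are wide compared with the shift. This also stands, so the figures above show a mechanism and do not estimate a bias.

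Third, a reader might take this factor to be the study's only look at drug interactions. It is not. SAP 5.4 also plans a ritonavir/cobicistat factor and a safety subgroup analysis of contraindicated patients on separately specified criteria. Those criteria are not in the documents, so whether they separate the exposures cannot be judged. SAP 8.2.3.4 also allows additional analyses.

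Fourth, the same patient appearing in two columns of the SOC/PT tables might be called double counting. With the overlap disclosed it is not an error; SAP 8.2.2.2 uses a similar overlapping breakdown for dose. The difference is that no risk ratio is planned there.

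Finally, SAP section 4 makes testing exploratory, with no significance level and no decision rules, and protocol 8.9 already lists the lack of a control group and limited handling of confounding. This limits the consequence but does not make the two exposures separable.

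**Conclusion.** The point holds as one of interpretation. With overlapping levels and unadjusted ratios, the precautions ratio cannot show whether precaution drugs alone carry more adverse reactions, the contraindications ratio has the mirror problem, and the two ratios are not independent. This follows from the level definitions for any non-zero overlap in which the second kind of drug changes the risk.

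The size is unknown. Under the illustrative assumptions of no precaution-drug effect and doubled or tripled risk in overlap patients, a true ratio of 1.00 becomes 1.05 to 1.40 across 5% to 20% overlap. The comparison with both absent rests on an inferred reference level. The documents do not support the stronger readings that the planned row is wrong for its label or that a material bias is present. Given the exploratory status, this is a worthwhile, inexpensive improvement to a safety table.

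**What to change.** In SAP 5.4 and both lists of 8.2.3.3:

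1. Keep the existing overlapping rows as descriptive totals, so that the figure for all precaution-drug users is not lost.
2. Add mutually exclusive levels: both absent; precaution drug only; contraindicated drug only; both. If either of the last two has fewer than 10 patients, merge them as any contraindicated drug and label the row so, since the merged ratio still carries precaution-drug effects.
3. Calculate the risk ratios on the exclusive levels, name both absent as the reference in words, and report the number of overlapping patients.
4. State the timing rule: classify by the co-drugs started on or before event onset or, for patients without an event, during the observation period. A reaction on a precaution drug that precedes a later contraindicated drug is then still counted. Without such a rule, moving the patient to a contraindicated level could leave that reaction counted nowhere.

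**Cost.** No new data are needed: protocol 8.3.6.1 already collects drug name and period of administration for all drugs used. The exclusive levels have smaller cells and wider intervals, and derivation is slightly more work. The timing rule gives patients with an event a shorter window for classification than patients without one. That should be noted with the table, and the SAP should say which onset applies when a patient has several reactions.
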